9.5 Missing and Spurious Data

All data collected under this study protocol will be included in the assessment of patient safety. Missing or incomplete AE data will assume greatest relationship to study drug and/or severity.

For the effectiveness endpoint analysis of all-cause mortality at Day 28 and 60 a sensitivity analysis will be performed for all participants that have been discharged from the hospital, cannot be reached via telephone contact, and their death status is not known. The sensitivity analysis will be performed where missing mortality status at Day 28 and 60 will be replaced as having died.

10 REGULATORY, ETHICAL AND LEGAL OBLIGATIONS

10.1 Declaration of Helsinki

The Principal Investigator will ensure that this Study is conducted in accordance with the most recent revision of the Declaration of Helsinki.

10.2 Good Clinical Practice

The Study will be conducted according to the study protocol and to Standard Operating Procedures (SOPs) that meet the guidelines provided by the International Conference on Harmonization (ICH) for Good Clinical Practice in clinical studies.

10.3 Institutional Review Boards/Ethics Committees

Before implementing this study, the protocol, the proposed patient informed consent forms and other information for the patients must be reviewed by a properly constituted committee or committees responsible for approving clinical studies. The IRB/IEC written signed approval letter/form must contain approval of the designated investigator, the protocol (identifying protocol title, date, and version number), and of the patient informed consent form (date, version).

Any change or addition to the protocol can only be made in a written protocol amendment that must be approved by the Sponsor, the IRB/IEC, and the Health Authorities.

10.4 Regulatory Authority Approval

Before this study is implemented, the protocol must be approved by the relevant regulatory authority.

10.5 Informed Consent

The investigator must fully inform the patient or patient's legally authorized representative of all pertinent aspects of the trial including the written information approved/favorably assessed by the IRB/IEC.

Prior to the start of the pre-study examination, the written informed consent form must be signed and personally dated by the patient, or the patient's legally authorized representative, and by the physician who conducted the informed consent discussion. One copy of the written information and signed consent form must be given to each patient or the patient's legally authorized representative, and one (1) copy must be retained in the investigator's study records.

10.6 Patient Confidentiality and Disclosure

Data on patients collected on eCRFs during the trial will be documented in an anonymous fashion and the patient will only be identified by the patient number, and by his/her initials. If, as an exception, it is necessary for safety or regulatory reasons to identify the patient, all parties are bound to keep this information confidential.

The investigator will guarantee that all persons involved will respect the confidentiality of any information concerning the trial patients. All parties involved in the study will maintain strict confidentiality to assure that neither the person nor the family privacy of a patient participating in the trial is violated. Likewise, the appropriate measures shall be taken to prevent access of non-authorized persons to the trial data.

10.7 Collection, Monitoring and Auditing Study Documentation, and Data Storage

10.7.1 Collection of Data and Monitoring Procedures

This study will use a 21 CFR Part 11 compliant electronic data capture system (EDC). An electronic case report form (eCRF) is used for data recording. All data requested on the eCRF must be entered and all missing data must be accounted for.

The data will be checked for completeness and correctness as it is entered by the real-time online checks applied by the EDC system. Off-line checks will also be run to perform any additional data review required. Discrepancy reports will be generated accordingly and transferred to the study center for resolution by the investigator or his/her designee.

Accurate and reliable data collection will be assured by verification and cross-check of the eCRF against the investigator's records by the study monitor (source document verification), and the maintenance of a study drug-dispensing log by the investigator.

Before study initiation, at a site initiation visit or at an investigator's meeting, a Sponsor representative will review the protocol and case report forms with the investigators and their staff. During the study a monitor will visit the site regularly to check the completeness of patient records, the accuracy of entries on the case report forms, the adherence to the protocol and to Good Clinical Practice, the progress of enrollment. The monitor will ensure during on-site visits that study medication is being stored, dispensed and accounted for according to specifications. Key trial personnel must be available to assist the monitors during these visits.

The investigator must give the monitor access to relevant hospital or clinical records, to confirm their consistency with the case report form entries. No information in these records about the identity of the patients will leave the study center. Monitoring standards require full verification for the presence of informed consent, adherence to the inclusion/exclusion criteria, documentation of SAEs and the recording of primary efficacy and safety variables. Additional checks of the consistency of the source data with the eCRFs are performed according to the study-specific monitoring plan.

10.7.2 Auditing Procedure

In addition to the routine monitoring procedures, the Sponsor or the regulatory authority can conduct an audit or an inspection (during the study or after its completion) to evaluate compliance with the protocol and the principles of Good Clinical Practice.

The investigator agrees that representatives of the Sponsor and Regulatory Authorities will have direct access, both during and after the course of this study, to audit and review all study-relevant medical records.

10.7.3 Retention of Documents

The investigator must maintain source documents for each patient in the study, consisting of all demographic and medical information, including laboratory data, and keep a copy of the signed informed consent form. All information on case report forms must be traceable to these source documents in the patient's file. Data without a written or electronic record will be defined before trial start and will be recorded directly on the case report forms, which will be documented as being the source data.

10.8 Disclosure of Information

All information provided to the investigator by Ampio Pharmaceuticals, Inc. or their designee, will be kept strictly confidential. No disclosure shall be made except in accordance with a right of publication granted to the investigator.

No information about this study or its progress will be provided to anyone not involved in the study other than to Ampio Pharmaceuticals, Inc or its authorized representatives, or in confidence to the IRB, or similar committee, except if required by law.

10.9 Discontinuation of the Study

Ampio Pharmaceuticals, Inc., may terminate the study at any time upon immediate notice from the Sponsor to all investigators for any reason, including the Sponsor's belief that discontinuation of the study is necessary for the safety of patients.

10.10 Study Report, Publication Policy and Archiving of Study Documentation

10.10.1 Study Report and Publication Policy

Depending on the outcome of the study, an ICH-compliant integrated clinical and statistical report may be prepared upon completion of the study and data analysis. The results of the study may also be published in a relevant peer-reviewed journal, with authorship status and ranking designated according to the acknowledged contributions of participating investigators, institutions and the Sponsor.

10.10.2 Study Documents

The investigator must maintain source documents for each patient in the study, consisting of all demographic and medical information, questionnaires, including laboratory data, etc., and keep a copy of the signed informed consent form. All information on the e-case report forms must be traceable to these source documents in the patient's file. Data without a written or electronic record will be defined before trial start and will be recorded directly on the e-case report forms, which will be documented as being the source data.

10.10.3 Archiving of Documents

Essential documents, as listed below, must be retained by the investigator for as long as needed to comply with national and international regulations. The Sponsor will notify the investigator(s)/institution(s) when the study-related records are no longer required. The investigator agrees to adhere to the document retention procedures by signing the protocol. Essential documents include:

- IRB/IEC/REB approvals for the study protocol and all amendments
- All source documents and laboratory records
- CRF copies (electronic copies on a CDROM)
- Patients' informed consent forms (with study number and title of trial)
- FDA form 1572
- Any other pertinent study document.

1. INTRODUCTION

This statistical analysis plan (SAP) outlines the proposed statistical methods to be implemented during the review of data to ensure that it confirms with categories determined by the CRF or the anticipated ranges for continuous variables and analysis of data collected within the scope of Clinical Protocol AP-017, “A Randomized, Double-Blinded, Placebo-Controlled Phase II Study to Evaluate the Safety and Efficacy of Intravenous Ampion in Adult COVID-19 Patients Requiring Oxygen Supplementation.”

It is not intended that each and every table, listing, or graph will be included in the clinical study report (CSR). It is also possible that additional analyses will be conducted after review of the data. Any analyses or summaries not specified in the SAP, but performed after review of the data, will be identified in the CSR as post hoc.

There will be an unblinded team responsible for obtaining the required material for the analysis from the study’s unblinded data manager (DM) for the clinical trial. The unblinded team will present the results of the interim analysis to the sponsor in a blinded fashion including whether there should be an increase in the sample size for the trial.

2. OBJECTIVES

The severe acute respiratory syndrome coronavirus 2 (SARS-CoV-2) has resulted in the pandemic spread of coronavirus disease 2019 (COVID-19), which has a high rate of infection, has a high rate of hospitalization, has overwhelmed healthcare systems, and can be fatal.

Ampion is the low molecular weight filtrate of human serum albumin with the *in vitro* ability to modulate inflammatory cytokine levels. Ampion has the potential to improve clinical outcomes for COVID-19 patients by reducing inflammatory cytokines correlated with the disease.

This study aims to evaluate Ampion and clinical outcomes in patients with COVID-19 who require supplemental oxygen. The data from this study will inform decisions for the Ampion clinical development.

2.1 Primary

The primary trial objective is to evaluate the effect of Ampion on prevention of need for mechanical ventilation or death prior to day 28 in adult participants with respiratory distress due to COVID-19.

2.2 Secondary

The secondary trial objectives evaluate the safety and efficacy of IV Ampion versus control in improving the clinical course and outcomes of participants with COVID-19 who require supplemental oxygen.

2.3 Study design

Statistical Analysis Plan (SAP) for Clinical Study AP-017

This is a Phase II randomized, double-blinded, placebo-controlled study to evaluate the safety and efficacy of IV Ampion in participants with COVID-19 who require supplemental oxygen.

Participants will be randomized 1:1 to active or placebo using a random allocation sequence stratified by disease severity.

All subjects receiving test product will also receive the standard of care (SOC) for COVID-19, which includes:

- Oxygen administration to maintain oxygen saturation of 90% or greater.
- Nursing physical that may include review of neurological; pulmonary; cardiac; gastrointestinal; and urinary assessment at least daily during treatment.
- Vital monitoring (heart rate, blood pressure, temperature, respiratory rate, SpO2) at least daily during treatment.
- Telemetry monitoring to evaluate heart rhythm and rate.
- Diet as tolerated to satisfy nutritional needs.
- Treatments for COVID-19 symptoms including antibiotics, cough suppressants/expectorants, anti-coagulants, fever reducers/pain killers, anti-nausea drugs, and/or bronchodilators.
- Treatments for COVID-19 as approved by the FDA including expanded access, emergency, or compassionate use (i.e., remdesivir, dexamethasone).
- Medications will be recorded as concomitant medication, tabulated, and compared among groups.

The clinical effects, safety, and tolerability of treatment will be evaluated from baseline to Day 28 and through Day 60. Evaluations at screening and during the 5-day treatment occur in person. Evaluations after the 5-day treatment to the end of the study (days 7 to 60) will typically occur via telephone contact unless the patient is in an inpatient setting.

2.4 Sample Size

The trial is designed to enroll up to approximately 200 patients across two treatment arms (active or control), with 100 subjects per arm, randomized 1:1 using a random allocation sequence stratified by COVID-19 disease severity (severe or critical). An interim analysis of the data is planned after 30 subjects (approximately n=15 subjects per arm) to evaluate the relative effect. At the interim analysis, the sample size may be re-estimated to determine the additional number of patients required for adequate power to meet the chosen effect size for the primary endpoint.

The number of participants is selected based on the effects observed for the primary endpoint, prevention of need for mechanical ventilation or death prior to day 28. A study recently reported in Lancet Respiratory Medicine with 243 hospitalized patients receiving the placebo for COVID-19 found 22% did not achieve day 28 ventilation-free survival (Lancet Respir Med 2021; [https://doi.org/10.1016/S2213-2600\(21\)00494-X](https://doi.org/10.1016/S2213-2600(21)00494-X)). In the AP-014 study, a lower rate (8%) was observed for subjects receiving inhaled Ampion. Assuming the same proportions (8% for Ampion and 22% for control) by Day 28, with 100 subjects per group, a two-sided 5% significance level, and using a z-test with unpooled variances, then under binomial enumeration the power to detect this difference is about 81.3%.

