4 SELECTION OF PARTICIPANTS

4.1 Number of Participants

The trial is designed to enroll up to approximately 200 patients across two treatment arms (active or control), with a 100 subjects per arm, randomized 1:1 using a random allocation sequence stratified by COVID-19 disease severity (severe or critical). An interim analysis of the data is planned after 30 subjects (n=15 subjects per arm) to evaluate the relative effect. At the interim analysis, the sample size may be re-estimated to determine the additional number of patients for adequate power up to the 200 subjects.

The number of participants is selected based on the effects observed for the primary endpoint. A study recently reported in Lancet Respiratory Medicine with 243 hospitalized patients receiving the placebo for COVID-19 found 22% did not achieve day 28 ventilation-free survival (Lancet Respir Med 2021; [https://doi.org/10.1016/S2213-2600\(21\)00494-X](https://doi.org/10.1016/S2213-2600(21)00494-X)). In the AP-014 study, a lower rate (8%) was observed for subjects receiving inhaled Ampion. Assuming the same proportions (8% for Ampion and 22% for control) by Day 28, with 100 subjects per group, a two-sided 5% significance level, and using a z-test with unpooled variances, then under binomial enumeration the power to detect this difference is about 81.3%.

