9.2.3 Interim Analysis

This trial is designed to enroll up to approximately 200 subjects, randomized to active or control, following an equal allocation to treatment arms. An interim analysis of the data is planned after 30 subjects (n=15 subjects per arm) to evaluate the relative effect. At the interim analysis, the sample size may be re-estimated to include additional subjects to attain adequate power up to a 200 total subjects. This will be conducted at an alpha level of 0.001 and thus the overall alpha level for the final test will be performed at $\alpha=0.047$ instead of $\alpha=0.05$. The sponsor also reserves the right to alter the final sample size if the assumptions of the death rates are not satisfied at this interim analysis.

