All binary outcomes are single incident percentages and thus the differences between the treatment groups will be tested using Fisher's exact test. The length of stay endpoints are also single incident endpoints the differences between the treatment groups will be tested using two sample t-test. All the other change from baseline variables are repeated assessments and will be analyzed utilizing a repeated measures analysis of variance.

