3. STUDY ENDPOINTS AND ANALYSES

Statistical Analysis Plan (SAP) for Clinical Study AP-017

3.1 Primary Endpoint:

The primary endpoint assesses the effect of Ampion compared to placebo on prevention of need for mechanical ventilation or death prior to day 28. This is measured as the occurrence of mechanical ventilation or death by Day 28.

Let π_A and π_S represent the rate of this outcome for Ampion and control during the first 28 days after randomization. Then it is desired to demonstrate that the mechanical ventilation and death rate for Ampion is different than the corresponding rate for the control. Formally, this is presented as:

$$H_0: \pi_A = \pi_S \text{ versus } H_A: \pi_A \neq \pi_S$$

This will be tested utilizing the appropriate chi-square test or Fisher's exact test utilizing PROC FREQ with the EXACT option, if necessary.

Also, the median time to mechanical ventilation or death will be tested for difference between the two groups via the log-rank test. The test will be performed using PROC LIFETEST. The time to event distributions in each group will be estimated using the method of Kaplan and Meier.

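### The 81.3% power is stated for an unpooled z-test at 0.05; for Pearson's chi-square at the final alpha it is 80.2% to 81.2%, and the plan does not fix the primary test

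*SAP*

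**What the plan says.** The power statement appears in protocol 4.1 and 9.1 and in SAP 2.4. Its inputs are: "Assuming the same proportions (8% for Ampion and 22% for control) by Day 28, with 100 subjects per group", "a two-sided 5% significance level", and a stated power obtained "using a z-test with unpooled variances, then under binomial enumeration the power to detect this difference is about 81.3" per cent.

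The primary analysis is worded identically in protocol 9.4.1 and SAP 3.1: "This will be tested utilizing the appropriate chi-square test or Fisher's exact test utilizing PROC FREQ with the EXACT option, if necessary". Neither section says which chi-square is meant (Pearson, continuity-corrected or stratified) or when Fisher's test becomes necessary.

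Protocol 9.4.2, which covers the secondary endpoints, adds: "All binary outcomes are single incident percentages and thus the differences between the treatment groups will be tested using Fisher's exact test".

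The final test is not run at 0.05. Of the interim look, protocol 9.2.3 says: "This will be conducted at an alpha level of 0.001", and it sets the final alpha at 0.047. SAP 6.1 uses the same interim level but puts the final alpha at about 0.049.

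**The concern.** The power figure describes a test that the analysis sections do not name, at an alpha that the final analysis will not use. The tests that the primary wording allows do not all have the same power, and their p-values can fall on opposite sides of the threshold. With the test and the alpha both unsettled, a borderline primary result could be called significant under one permitted combination and not under another. The figure that justifies 100 patients per arm should be the power of the test that will be run, at the level at which it will be run.

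**Working it through.** **Inputs.** Event rates of 8% and 22%, 100 per arm, two-sided 0.05 (SAP 2.4); final alpha 0.047 (protocol 9.2.3) or 0.049 (SAP 6.1).

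**Method.** For x Ampion and y control events, sum over all 101 × 101 outcomes:

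power = Σ Σ Bin(x; 100, 0.08) · Bin(y; 100, 0.22) · 1{p(x, y) ≤ α}

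With a = x/100, b = y/100 and p̄ = (x + y)/200, the tests are:

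- Unpooled z: (b − a) / √[a(1−a)/100 + b(1−b)/100]
- Pearson chi-square: square of (b − a) / √[2p̄(1−p̄)/100]
- Continuity-corrected chi-square: as Pearson, with |b − a| reduced by 1/100
- Fisher: the two-sided exact p-value

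**Results (exact power)**

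| Test | α = 0.05 | α = 0.049 | α = 0.047 |
|---|---|---|---|
| Unpooled z | 81.3% | 81.3% | 81.2% |
| Pearson chi-square | 81.3% | 81.2% | 80.2% |
| Continuity-corrected | 74.2% | 74.2% | 74.0% |
| Fisher | 75.8% | 74.9% | 74.2% |

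1. **The plan's figure reproduces.** The unpooled z-test at 0.05 gives 81.28%.
2. **The change of test alone costs nothing.** Pearson at 0.05 also gives 81.28%.
3. **The change of alpha costs little.** For Pearson, 81.28 − 81.17 = 0.11 points at 0.049, and 81.28 − 80.19 = 1.09 points at 0.047.
4. **Fisher would cost 6 to 7 points.** 81.3 − 74.9 = 6.4 at 0.049, and 81.3 − 74.2 = 7.1 at 0.047. Fisher's power is just under 80% at 112 per arm and about 80.8% at 114. The cause is conservatism: at a common 15% rate and nominal 5%, its actual size is 3.3%.
5. **The design does not call for Fisher.** The pooled rate is (8% + 22%)/2 = 15%, or 15 expected events per arm. Suppose Fisher were triggered by an expected cell count below 5 (an assumption, since the documents give no threshold). That needs fewer than 10 events in total, which at the design rates has probability of about 0.0000014, or 1 in 700,000.
6. **The open choice can decide the result.** Pearson rejects and Fisher does not in 6.3% of trials at 0.049 and 6.0% at 0.047. The reverse never occurs.
   - 8 versus 18 events: p̄ = 0.13, z = 0.10/√(2 × 0.13 × 0.87/100) = 2.103. Pearson p = 0.036; Fisher p = 0.057.
   - 10 versus 20 events: p̄ = 0.15, z = 0.10/√(2 × 0.15 × 0.85/100) = 1.980. Pearson p = 0.0477, which is significant at the SAP's 0.049 and not at the protocol's 0.047.

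**The case against.** The strongest reply is that nothing in the arithmetic is wrong. The 81.3% is correct for the test, alpha and method stated. At 0.05 it is also the power of Pearson's test, the natural reading of the first-named option, and at either final alpha that test keeps at least 80%. Making Fisher conditional is conventional wording for sparse tables, and sparse tables are not a realistic prospect here. All of this stands, and it limits the size of the point.

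A reader might go further and infer from the sentence on binary outcomes in protocol 9.4.2 that Fisher is prescribed for the primary endpoint, so that true power is 74% to 75%. The documents do not support that. The sentence sits under Secondary Endpoints, beside the methods for length of stay and change from baseline. The primary endpoint has its own sections (protocol 9.4.1, SAP 3.1), which put chi-square first and Fisher second. Protocol 9.1 leaves analysis details to the SAP. The broad wording in 9.4.2 adds ambiguity and no more.

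The reply leaves three gaps open: no rule for invoking Fisher, no statement of which chi-square is meant, and two final alphas, neither of which is the one used for power.

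**Conclusion.** The concern holds as a moderate correction. The stated power is high by about 0.1 points (alpha 0.049) to 1.1 points (alpha 0.047) for Pearson's chi-square. Power of 74% to 75% follows only if Fisher or a continuity-corrected test is chosen, which the wording allows but the expected counts do not require. The larger practical issue is that the primary test and its threshold are not uniquely fixed, and at the design rates the choice between Pearson and Fisher changes the conclusion in about 6% of trials. None of this shows an underpowered trial.

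The figures assume the design rates of 8% and 22%, exactly 100 analysed per arm, and an unstratified test. They ignore dropout, the interim look itself and any sample-size re-estimation.

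**What to change.** - In protocol 9.4.1 and SAP 3.1, name the uncorrected Pearson chi-square as the single primary test and remove the Fisher alternative for this endpoint.
- In protocol 9.4.2, limit the sentence on binary outcomes to the secondary endpoints, and align it with SAP 3.2.3 and 3.2.4, which allow chi-square or Fisher for the secondary binary endpoints.
- Reconcile the final alpha between protocol 9.2.3 and SAP 6.1. The SAP value equals 0.05 − 0.001; the protocol does not show how it reached 0.047.
- In protocol 4.1 and 9.1 and SAP 2.4, restate power for Pearson at the agreed alpha: 81.2% at 0.049 or 80.2% at 0.047. If Fisher is kept instead, state 74.9% or 74.2%. If a test stratified by severity is preferred, it needs its own power calculation, because these figures do not cover it.

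The cost is wording in both documents and no additional patients. There are two small downsides. The stated power falls slightly. Pearson's exact size also runs a little above nominal, at about 5.05% to 5.2% at nominal 5% for common event rates of 8% to 22%.
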